- 8. Patients with active viral (any etiology) hepatitis are excluded. However, patients with serologic evidence of chronic HBV infection (defined by a positive hepatitis B surface antigen test and a positive anti-hepatitis core antigen antibody test) who have a viral load below the limit quantification (HBV DNA titer <1000 cps/mL or 200 IU/mL) and are not currently on viral suppressive therapy may be eligible and should be discussed with the Medical Monitor. Patients with a history of HCV infection who have completed curative antiviral treatment and have a viral load below the limit of quantification may be eligible.
- 9. Diagnosis of other active invasive cancers other than the one treated in this study within 2 years prior to first study drug administration; Exceptions include appropriately treated basal cell or squamous cell skin cancer, or in situ carcinoma of uterine cervix, or other local tumors considered cured by local treatment.
- 10. Prior history of allergic reaction to the composition/excipients of AC699.
- 11. Psychological, familial, sociological, or geographical conditions that do not permit compliance with the protocol and/or follow-up procedures outlined in the protocol.

Statistical Methodology:

A 3+3 dose escalation design will be used. Some dose levels may be further expanded to approximately 20 patients to further characterize efficacy, safety, and or PK.

Safety Analysis:

Standard safety assessments will be performed regularly for all patients in the full analysis set (FAS)/safety analysis set (SAS) population during the entire course of the study. Safety will be assessed through the analysis of the reported incidence of treatment-emergent and treatment-related AEs. All AEs will be graded according to NCI CTCAE Version 5.0 and coded using Medical Dictionary for Regulatory Activities (MedDRA) version 25.0 or more recent. In addition, summaries of serious adverse events (SAEs), AEs leading to treatment discontinuation and dose modifications, AEs by maximum NCI CTCAE grade, and AEs related to study treatment will also be collected. Other safety endpoints, including laboratory results will be summarized for all patients in the SAS.

CONFIDENTIAL

Study Drug: AC699 Sponsor/Development Innovations Study Numbers: AC699-001/BRE 401

Efficacy Analysis:

- ORR, defined as the proportion of patients with confirmed CR or PR according to the RECIST Version 1.1 criteria.

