2. STUDY OBJECTIVES AND ENDPOINTS

Table 1 Study Objectives and Corresponding Endpoints

Primary Objective:	Endpoint/Variable:
Evaluate the safety and tolerability of AC699	Incidence and severity of dose-limiting toxicities (DLTs), treatment-emergent adverse events (TEAEs), and clinically significant Grade 3 or higher laboratory abnormalities
Secondary Objectives:	Endpoint/Variable:
Evaluate the preliminary anti-tumor activity of AC699	Objective response rate (ORR [CR+PR]) as defined by Response Evaluation Criteria in Solid Tumors (RECIST) Version 1.1, clinical benefit rate (CBR) (complete response [CR]+partial response [PR]+stable disease [SD] \geq 24 weeks), duration of response (DOR), disease control rate (DCR), and progression-free survival (PFS)
Characterize the pharmacokinetic (PK) profile of a single dose and after multiple doses of AC699	PK parameters
Exploratory Objectives:	Endpoint/Variable:
Evaluate the pharmacodynamic (PDx) effect of AC699 in ER α degradation	Change of ER α expression in tumors from baseline to post-treatment if tumor tissue is available from paired biopsies
Evaluate the relationship between circulating tumor cells (CTCs) count and administration of AC699	Correlation between CTC count at baseline and post-treatment, and anti-tumor activity (ORR, CBR, DOR, DCR, and PFS)
Evaluate the relationship between estrogen receptor gene 1 (ESR1) mutation status and antitumor activity of AC699	Correlation between ESR1 mutational status and anti-tumor activity (ORR, CBR, DOR, DCR, and PFS)
Evaluate the relationship between circulating tumor DNA (ctDNA) levels and anti-tumor activity of AC699	Correlation between ctDNA levels at baseline & post-treatment and anti-tumor activity (ORR, CBR, DOR, DCR, and PFS)

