A cumulative incidence of any of the following treatment-related events will trigger a hold on further patient enrollment for all dose cohorts until the SRC determines if it is safe to continue:

- Grade 4 adverse events (AEs) > 25%,
- Serious adverse events (SAEs) > 25%,
- AEs leading to discontinuation from study > 25%,
- Grade 5 AEs > 10%.

The 3+3 dose-escalation procedure is shown in Table 2.

CONFIDENTIAL

Study Drug: AC699 Sponsor/Development Innovations Study Numbers: AC699-001/BRE 401

Table 2 Dose-Escalation (3+3) Design

Number of Patients with a DLT	Action
0 of 3 patients	Escalate to next dose level
1 of 3 patients	Accrue additional evaluable patients at the current dose level (for a total of up to 6 evaluable patients) ^a
1 of 6 patients	Escalate to the next dose level
2 or more patients in a dose level group of up to 6 patients	The MTD has been exceeded

DLT = dose-limiting toxicity, MTD = maximum-tolerated dose

Dose-Limiting Toxicity

Toxicity will be assessed using the NCI CTCAE Version 5.0 unless otherwise specified. Dose-limiting toxicities thought to be related to AC699 during the DLT period (first 28 days) will be defined as any of the following toxicities if considered at least possibly related to study treatment, i.e., not attributable to the disease or disease-related process under investigation, or other non-study related explanation, and that means at least 1 of the hematologic or non-hematologic criteria below:

Dose-limiting toxicities (DLTs) will be defined as follows:

• Any Grade 5 toxicity

Hematological:

- o Grade 4 neutropenia for >7 days; or febrile neutropenia (ANC <1000/mm³ with a single temperature of >38.3° C [101° F] or a sustained temperature of ≥ 38° C [100.4° F] for more than 1 hour)
- o Grade 4 thrombocytopenia; or Grade 3 thrombocytopenia associated with clinically significant bleeding, including any bleeding that warrants a platelet transfusion
- o Grade 4 anemia (life-threatening consequences requiring urgent interventions)

• Non-hematological:

- o Grade 3 or 4 non-hematologic toxicity, with the **exception of**:
 - Alopecia;
 - Grade 3 nausea, vomiting, or diarrhea if well-controlled by supportive care within 72 hours;
 - Grade 3 skin rash that improves in ≤7 days, with or without supportive care;
 - Grade 3 fatigue that improves in ≤ 7 days, with or without supportive care;
 - Grade 3 endocrinopathies that only require treatment with hormone replacement therapy;

CONFIDENTIAL

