Sponsor/Development Innovations Study Numbers: AC699-001/BRE 401

Final Protocol: 07 May 2024 Version 4.0

^a For a patient to be considered "evaluable," he or she must have met the minimum safety evaluation requirements of the study, and/or experienced a DLT.

- Grade 3 non-hematologic laboratory abnormalities, other than liver function tests, will not be considered a DLT unless they are associated with clinical manifestations which lead to medical intervention and/or hospitalization
- Potential drug-induced livery injury consistent with Hy's Law (Appendix E),
 defined as AST and/or ALT > 3 × ULN with concurrent total bilirubin > 2 × ULN
 without findings of cholestasis (alkaline phosphatase [ALP] >2 × ULN)
- Grade 3 or higher electrolyte abnormality that lasts > 72 hours, unless the patient
 has clinical symptoms, in which case all Grade 3 or higher electrolyte abnormality
 regardless of duration should count as a DLT

Determination of Dose-Limiting Toxicities

The patient population used for determination of DLTs will consist of patients who have met the minimum safety evaluation requirements of the study, and/or who have experienced a DLT. Minimum safety evaluation requirements will be met if, during Cycle 1 of treatment, the patient receives at least 75% of planned total doses of AC699, completes all required safety evaluations, and is observed for at least 28 days following the first dose of AC699. Patients who have experienced a DLT may be allowed to continue treatment at a lowered dose, if in the opinion of the Investigator, Medical Monitor, and Sponsor, they continue to derive benefit.

Patients who discontinue treatment early due to disease progression or withdrawal will be asked to have all EOT safety evaluations performed as described in the protocol (see Section 7.6). If a patient withdraws from treatment during Cycle 1 due to any reason other than DLT and does not meet the minimum requirements for DLT assessment, that patient will be replaced.

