10.4.3 Safety Analysis

Safety will be assessed through the analysis of the reported incidence of treatment-emergent AEs. Treatment-emergent AEs are those with an onset on or after the initiation of therapy and will be graded according to NCI CTCAE Version 5.0.

The AEs will be coded using the current version of Medical Dictionary for Regulatory Activities (MedDRA; https://www.meddra.org/about-meddra/) and summarized using system organ class and preferred term by dose level for all patients in the Safety set/population. In addition, summaries of SAEs, AEs leading to treatment discontinuation, AEs by maximum NCI CTCAE grade, and AEs related to study treatment will also be presented by dose level.

Other safety endpoints, including laboratory results, vital signs, and ECG findings, will be summarized for all patients in the Safety set.

Concomitant medications will be coded using the World Health Organization Drug Dictionary (WHO DD; https://www.who-umc.org/), and they will be listed and summarized by dose level.

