5.2.4 Progression-Free Survival

PFS (months) is the time from date of first dose of AC699 to the first documentation of disease progression or death due to any cause. Participants who have neither progressed nor died will be censored.

Refer to Table 4 for the event/censoring rules and dates to be used.

Table 4: Progression Situations and Event/Censoring Rules

Situation	Date of Event or Censoring	Outcome
No baseline assessment	Date of first dose of AC699	Censored

Situation	Date of Event or Censoring	Outcome
Progression documented between scheduled visits, or after one missed or non-evaluable assessment	Date of progression (see Table 2)	Event
No progression	Date of last evaluable tumor assessment (see Table 2)	Censored
Treatment discontinuation for undocumented progression (e.g., clinical progression based on investigator claim)	Date of last evaluable tumor assessment (see Table 2)	Censored
Treatment discontinuation for adverse event or other reason	Date of last evaluable tumor assessment (see Table 2)	Censored
Further anticancer therapy started	Date of last evaluable tumor assessment (see Table 2)	Censored
Death before first PD assessment	Date of last evaluable tumor assessment (see Table 2)	Event (PFS)
Death before the next scheduled tumor assessment, or after one missed tumor assessment	Date of death (see Table 2)	Event (PFS)
Death, or progression after two or more missed tumor assessments	Date of last evaluable tumor assessment (see Table 2)	Censored

The rule to determine whether there are at least two missing tumor assessments is based on the interval between the last evaluable tumor assessment date and the event date. If the interval is greater than twice the protocol-specified interval between the tumor assessment plus the protocol-allowed time window around the assessment, then the number of missing assessments is two or more.

For the first 52 weeks, tumor assessments are to be performed every 8 weeks (\pm 5 days); therefore, the threshold will be 18 weeks. After the first 52 weeks, tumor assessments are to be performed every 16 weeks (\pm 5 days); therefore, the threshold will be 34 weeks.

6 Safety Analysis

All safety data will be presented in listings. Tables and figures will be presented as applicable.

Exposure to Study Treatments

Exposure to AC699 will be summarized in the following ways:

- Total Treatment Duration (days), calculated as *Date of Last AC699 Dose Date of First AC699 Dose + 1*.

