6.2 Adverse Events

A TEAE is defined as an AE with an onset or worsening grade on or after the first dose of study treatment up to 30 days after the end of treatment or up to the start of other anticancer

therapy (which occurs earlier). AEs will be graded using the National Cancer Institute - Common Terminology Criteria for Adverse Events (CTCAE) version 5.0 where applicable and coded using MedDRA version 25.0 or higher.

An overall summary of on treatment AEs will present the frequency and percentage of participants by the following categories:

- Any TEAEs
- Any AC699-related TEAEs
- Any grade ≥3 TEAE
- Any AC699-related grade ≥3 TEAE
- Any TEAE leading to death
- Any AC699-related TEAE leading to death
- Any treatment-emergent serious adverse events (SAE)
- Any AC699-related treatment-emergent SAEs
- Any TEAE leading to discontinuation of AC699
- Any TEAE leading to interruption of AC699
- Any TEAE leading to reduction of AC699

Additional summaries for all of the above categories, will present the frequency and percentage of participants experiencing at least one event by MedDRA SOC and MedDRA preferred term (PT).

Additional summaries for the following categories will present the frequency and percentage of participants experiencing at least one event by MedDRA SOC, MedDRA PT, and worst CTCAE grade:

- Any TEAEs
- Any AC699-related TEAEs

Specific listings, with all relevant information, will be provided for TEAEs, SAEs, TEAEs with an outcome of death, and TEAEs leading to discontinuation of AC699.

6.3 **Participant Deaths**

Death and primary cause of death will be summarized by frequency and percentage.

All death data will be provided in listings.

6.4 **Laboratory Parameters**

Descriptive statistics for each lab parameter (chemistry, hematology, urinalysis, and coagulation) at baseline, each scheduled post-baseline assessment, and changes from baseline to scheduled post-baseline assessments will be presented.

Abnormal laboratory values will be graded according to CTCAE version 5.0, if applicable. Clinical descriptions will not be considered when grading; grading will only be based on numeric results and thresholds.

A shift table will be presented for each laboratory parameter to display the shift from baseline to the maximum post-baseline CTCAE grade within 30 days post-treatment, inclusive of unscheduled post-baseline assessments. For parameters that can be graded in either direction

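### SAP 6.2 shows TEAEs by dose level only as crude percentages over patient-specific windows, so for events that keep accruing, toxicity is mixed with time on drug

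*Protocol*

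**What the plan says.** The protocol synopsis, under its safety analysis, states the measure: "Safety will be assessed through the analysis of the reported incidence of treatment-emergent and treatment-related AEs". That sentence sets neither a window nor a denominator; other sections do.

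The primary endpoint in Protocol Section 2 has three parts: "Incidence and severity of dose-limiting toxicities (DLTs), treatment-emergent adverse events (TEAEs), and clinically significant Grade 3 or higher laboratory abnormalities". Their observation periods differ.

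- **DLTs.** Protocol 5.1 counts them over the first 28 days. Unless a DLT occurs, a patient is evaluable only if she receives at least 75% of planned Cycle 1 doses, completes the safety evaluations and "is observed for at least 28 days following the first dose of AC699".
- **TEAEs.** SAP 6.2 counts events with onset or worsening "on or after the first dose of study treatment up to 30 days after the end of treatment". The window closes sooner if a new cancer treatment begins. Treatment itself is open-ended: footnote a of the Schedule of Assessments lets it continue while the investigator sees clinical benefit.

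The TEAE statistic is a proportion: "An overall summary of on treatment AEs will present the frequency and percentage of participants by the following categories". The breakdowns by system organ class, preferred term and worst grade use the same statistic. SAP 3.4.5 presents summaries by dose level and overall unless stated otherwise. Protocol 10.4.3 likewise tabulates AEs by dose level and adds that "AEs related to study treatment will also be presented by dose level".

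Exposure is a separate summary. SAP Section 6 gives "Total Treatment Duration (days), calculated as" last dose date minus first dose date plus one, with actual exposure and relative dose intensity. None of these is used as a denominator for adverse events. Neither document plans a common-window TEAE table, a time-to-first-event estimate or an exposure-adjusted rate.

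**The concern.** A crude percentage answers how many patients had the event at some time while watched, and here the watching time is set by the patient's own treatment. Time on drug can differ between dose levels for reasons unrelated to event risk. Activity may differ by dose, and Protocol 5.1 requires a documented ESR1 mutation for backfill patients but not for the initial escalation cohorts, with only selected doses backfilled.

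A dose on which patients stay longer gives each patient more time to have a late or steadily accruing event. Its percentage rises even if its monthly risk equals that of its neighbour.

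The RP2D may be any dose up to the MTD (Protocol 5.1.3). Among doses that pass the DLT rule, the TEAE tables are a main place where a reader would look for tolerability differences, and as planned they do not separate risk from observation time.

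**Working it through.** The documents state no TEAE rate, treatment duration or power, so there is no planned figure to reproduce. The check asks how large the effect is under stated assumptions.

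**Inputs**
- Window: time on drug plus 30 days (SAP 6.2), taken as 1 month.
- Patients per expanded dose: about 20 (Protocol 10.1). SAP 2.1 still says about 15; the protocol figure is used.
- Assumed: the same constant hazard *h* of a first event at both doses; exponential time on drug with median *m* months, so λ = ln 2 / *m*; stopping independent of the event.

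**Expected crude percentage**

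P = 1 − e^(−h) × λ/(λ + h)

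For h = 0.05 per month:
- m = 3: λ = 0.2310; P = 1 − 0.9512 × 0.2310/0.2810 = 1 − 0.9512 × 0.8221 = 21.8%
- m = 8: λ = 0.0866; P = 1 − 0.9512 × 0.0866/0.1366 = 1 − 0.9512 × 0.6341 = 39.7%

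| Hazard per month | Medians (months) | Crude % |
|---|---|---|
| 2% | 3 vs 8 | 9.8 vs 20.4 |
| 5% | 3 vs 8 | 21.8 vs 39.7 |
| 10% | 3 vs 8 | 36.8 vs 58.0 |
| 5% | 4 vs 8 | 26.2 vs 39.7 |
| 5% | 2 vs 4 | 16.9 vs 26.2 |

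**Chance of a visible gap.** With 20 patients per dose, 15 points is 3 patients. Summing the exact binomial probabilities that the longer-treated dose has at least 3 more patients with an event, at h = 5%:

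| Medians (months) | Unequal durations | Equal durations |
|---|---|---|
| 3 vs 8 | 65% | 17% (both 3) to 21% (both 8) |
| 4 vs 6 | 36% | 18% to 20% |
| 3 vs 4 | 27% | 17% to 18% |

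**Where the effect disappears**
- All risk in the first 28 days (about 30% of patients affected): crude figures at medians of 4 and 8 months are 30.0% and 30.1%.
- Near-universal events (hazard 1.0 per month): 94.5% and 97.0% at 4 and 8 months.

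**What the alternatives give**
- Common window, h = 5%: Days 1-28 gives 1 − exp(−0.05 × 28/30.4375) = 4.5% at both doses. By Day 84 the figure is 1 − exp(−0.05 × 84/30.4375) = 12.9% at both.
- Follow-up for later time points: the share of TEAE windows closing before Day 56 is 1 − exp(−λ × 26/30.4375), which is 18% at a 3-month median and 7% at 8 months. A simple proportion at Day 56 would therefore be biased by short follow-up, and a censored estimate is needed.
- Exposure-adjusted first-event rate: about 5 per 100 patient-months at both doses under a constant hazard. If all risk (about 30%) falls in month 1, two identical doses with medians of 3 and 8 months give about 7.8 and 3.4, and the longer-treated dose wrongly looks safer.

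**The case against.** The strongest reply is that this is a descriptive Phase I study. SAP 2.4 and 3.1 exclude hypothesis testing, no safety comparison between doses is specified, and no rule ties the RP2D to a TEAE percentage. The Safety Review Committee sees all available safety data and takes dose interruptions and reductions into account. All of that stands. A reader might infer that the plan formally compares doses on the crude percentage, or that the RP2D is driven by it. The documents support only that the tables are shown side by side by dose level and are among the data that may be used.

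A reader might also infer that the whole primary endpoint is distorted. It is not: the DLT part, on which escalation and the MTD rest, has a common 28-day period.

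Nor does every difference in duration distort every TEAE figure. The effect needs events that keep accruing, and the constant hazard used above is the case that produces it. In a first-in-human study the onset pattern is not known beforehand.

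It is also tempting to say that a dose abandoned early will look safer. That does not follow when patients stop for toxicity, because the event that stopped them is already in the numerator and in the category for TEAEs leading to discontinuation.

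Finally, treatment duration is tabulated by dose level and all safety data are listed, so an imbalance would be visible. Separate aggregate tables still do not let a reader derive common-window incidence.

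**Conclusion.** The concern holds in limited form. Outside DLTs, the planned TEAE summaries are crude percentages over windows of unequal length, and no planned table puts dose levels on a common time base. For accruing events, equal toxicity with unequal time on drug gives unequal expected percentages: 22% versus 40% in the main illustration, with a gap of 15 points or more in about 65% of trials of 20 patients per dose against 17-21% with equal durations. With medians of 3 versus 4 months the chance is only 27%.

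These sizes rest on assumed hazards and durations, a constant hazard, and stopping unrelated to the event. The documents fix the mechanism but not its size. This is a gap in descriptive reporting that is cheap to close. It does not invalidate the dose-escalation rules or the MTD.

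**What to change.** In SAP 6.2, keep the crude tables and add, by dose level:

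1. Incidence of any TEAE, related TEAEs, Grade ≥3 TEAEs and serious TEAEs in Days 1-28. The 30-day tail covers this window for nearly all patients, even those who stop early.
2. Time-to-first-event cumulative incidence, for example at Day 56 and Day 84, for Grade ≥3 TEAEs, serious TEAEs and TEAEs leading to discontinuation, censoring at the end of the TEAE window. State how death without a prior event is handled.

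Exposure-adjusted first-event rates with exact Poisson confidence intervals may be added as supportive only, because they assume a constant hazard and mislead when events cluster early.

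Two sentences complete the change. Any descriptive dose-to-dose statement about TEAE frequency should cite the common-window or cumulative-incidence table alongside the crude one. In the added tables, patients are grouped by starting dose with follow-up cut at any intra-patient dose escalation: Protocol 5.1.2 permits such escalation, and the actual-dose rule in SAP 3.3 does not say where later events go.

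The cost is SAP wording and a few tables from AE and dosing dates already collected. The Days 1-28 table does not show later-onset toxicity; the crude and cumulative-incidence tables cover that.

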1. INTRODUCTION

1.1 Background and Study Rationale

The American Cancer Society indicates that the average risk of a woman in the United States developing breast cancer in her life is approximately 13%, and that about 43,250 women will die from breast cancer in 2022 (ACS 2022). Estrogen receptor (ER)α, encoded by ESR1, is a hormone-regulated transcription factor that plays a critical role in breast cancer initiation and proliferation. Modulation of estrogen activity and/or synthesis with therapeutics such as tamoxifen and letrozole has been the mainstay therapeutic strategy for ER-positive breast cancer (Sledge et al. 2014).

Nearly 80% of breast cancers express estrogen receptors (ER), hormone-regulated transcription factors (DeSantis et al. 2019) and both preclinical and clinical studies highlight an important oncogenic role for estrogen and ERs mediated through proliferation and survival pathways (Spicer and Pike 1993). Several ER-directed therapies have been developed to antagonize the oncogenic ER function in patients with locally advanced, recurrent, or metastatic cancer. These include selective ER modulators (SERMs), selective steroidal and nonsteroidal aromatase inhibitors, and selective ER degraders (SERDs) such as fulvestrant (Beslija et al. 2009; Robertson 2002). SERDs hold great promise as treatment options as they have been shown to inhibit ER activity as well as decrease ER expression (DeFriend et al. 1994; Jones and Pippen 2005). Until 2023, fulvestrant was the only US Food and Drug Administration (FDA)-approved SERD. Fulvestrant is indicated for the treatment of patients with metastatic or advanced hormone-positive (HR+) breast cancer (Wang 2020) and has validated the important link between ER degradation and disease control. However, there are several disadvantages associated with fulvestrant. It is administered via intramuscular injection which necessitates a clinical visit for every dose. This route of administration contributes to poor drug exposure; hence it appears to limit efficacy. It has also been reported that up to 50% of ER baseline levels remained after 6 months of fulvestrant treatment (Robertson and Harrison 2004). In 2023, an oral SERD, elacestrant, was approved by the FDA for the treatment of ER-positive, HER-2 negative, ESR1 mutated advanced or metastatic breast cancer (FDA 2023). There are currently additional SERDs in clinical development including GDC9545, AZD9833, SAR43989, rintodestrant, and ZN-C5. In addition to SERDs, a newly emerging technology, E3 ligaseengaged chimeric degraders, has been used to induce more potent and deeper ER degradation. Chimeric degraders degrade a protein of interest (POI) by connecting a POI ligand to an E3recruiting ligand with an optimal linker. This subsequently brings the POI within close proximity of E3 ligase and induces subsequent robust POI ubiquitination and degradation. Chimeric ER degraders can degrade the ER protein without the risk of signal activation (Nalawansha and Crews 2020; Mottamal et al. 2021). Furthermore, the chimeric ER degraders are not degraded along with the target protein and as such can be recycled within a cell. This potentially allows chimeric ER degraders to achieve potent ER degradation and treatment efficacy at a much lower drug concentration with lower associated toxicities. Investigational chimeric ER degraders are currently in early stages of clinical development. Although preliminary and encouraging safety and efficacy data have been observed, none of them have been authorized by the FDA for marketing purposes.

CONFIDENTIAL

Sponsor/Development Innovations Study Numbers: AC699-001/BRE 401

Final Protocol: 07 May 2024 Version 4.0

